### ***Goal and procedures for Aim 3***

Supplement Aim 3 will add an additional 25 COVID-positive LIFT recipients to the 75 included in the parent U01's Aim 3, with the goal of understanding barriers and facilitators to the successful use of the LIFT app in a pandemic. We will use a stratified purposive design to sample 25 participants, a number sufficient for

theme saturation. The procedures will include a 30-minute semi-structured telephone interview conducted by an experienced coordinator to explore app access, content, and use. Theoretical sampling will ensure variability in potentially influential characteristics: response to LIFT (high vs. low), demo-graphics (age, race, gender), and baseline distress (moderate vs. high). Analyses will be nearly identical to the U01 and will use modified grounded theory methods (e.g., open and axial coding, consensus building on codes, member checking) to inductively and iteratively develop frameworks.

### ***Sample size and power considerations***

For Supplement Aim 1, we will randomize 300 patients. Even with a 40% dropout rate (i.e., 180 at 3 months) and conservative assumptions (SD=6.0,  $p=0.5$ , two-sided test, type-I error of 5%), this sample size will provide a power of 80% to detect a differential between-group PHQ-9 improvement at 3 months as small as 2.5 units, substantially less than the minimal clinically important difference (MCID) of 5.0 units. Calculations were based on mixed-models tests for a difference in slopes using PASS 16 Software (v16.0.5; Kaysville UT).

**11. Subject Participation Duration:** It will require 5 months for participants to complete the entire study from the time of randomization, including the month-long intervention and follow up surveys.

**12. Study Duration:** We estimate that from the time the RCT opens to enrollment it will require 1 year to complete all study activities.

**13. Costs to the Subject:** There are no costs to participants.

### **14. Compensation**

Participants will receive \$20 for each completed survey, up to a total of \$60, for participation in the LIFT COVID study.

### **15. Risk-benefit assessment**

#### ***Potential risks***

It is possible that participants could experience a breach of privacy should their records be accessed unlawfully by an outside party. Also, it is possible that participants may experience mild anxiety when answering survey questions, though we have not observed this in similar interventions such as LIFT or CSTEP. However, we believe that involvement in this study will present no significant physical, psychological, financial, legal, or other risks. Additionally, there is always the potential of a breach of data security, as is noted in any IRB-approved consent form. However, we have a number of security features to protect these data that will be described below in Section 2.

#### ***Adequacy of protection against risks***

##### **Recruitment and informed consent procedures**

First, the Duke Institutional Review Board (IRB) will review and approve the study protocol before study initiation (as they did for our preliminary work conducted under Duke IRB Protocols #00062340, #00069031, and #00071161). Informed consent (verbal, e-consent, or written) will be required from all participants. Second, we will use a standardized screening and enrollment protocol that respects participant privacy and rights. Clinical research coordinators will approach patients to discuss the study at the time the BLUE CORAL participant is on the phone completing a BLUE CORAL survey. This will be possibly be aided by a short IRB-approved recruitment video we have produced and piloted for LIFT, similar to other highly rated videos our group has made for similar purposes in other clinical trials. After following the verbal consent script, the clinical research coordinator will then obtain verbal informed consent from the participant. If a patient wishes to do e-consent, this procedure will be followed as described above in Section 6.B. Potential subjects will have up to 72 hours to consider enrollment. For the clinical trial, we will take great care to present the treatment group

assignment possibilities ("like drawing a number out of a hat") tactfully and with clearly stated equipoise in person, as we have done successfully in past ICU-based clinical trials. A copy of the consent form will be emailed or mailed to participant (as they prefer) and the original maintained in the study data system (e-consent) or in a secure location at the study site (mailed consent). The study team will provide contact information for the PI.

### Protections against risk

#### *General oversight*

There are several ongoing mechanisms for monitoring the occurrence of adverse events. The University of Michigan, Duke, Colorado, and Oregon investigators will perform day-to-day monitoring of the study activities at their sites as they have done in many other trials and studies involving similar participants. The Principal Study Investigator, [name], has demonstrated in research to date involving nearly 1,500 participants that he keeps careful records of patients' whereabouts and health status. Careful monitoring of all persons entering the study will minimize attrition and will ensure the clinical safety of these patients. This monitoring is facilitated by a telephone number (PI's cell phone) and email address ([contact]) provided to participants upon entry into the study to report concerns related to study participation, weekly meetings between the clinical research coordinators and co-investigators to discuss study progress and any adverse events, and direct supervision of the study by the PIs.

#### *Plans to prevent coercion of patients and to ensure voluntary participation*

We will strive to create an environment free of any coercive practices for patients. We will stress that study involvement is absolutely voluntary and that choosing to participate or not participate will not affect their care in anyway. In addition, we will utilize the standardized 2-minute informational video ([lift.duke.edu/COVID](http://lift.duke.edu/COVID)), which has been used successfully in the LIFT trial to describe treatment groups and ensure a similar approach across sites.

#### *Specific longitudinal participant oversight plans for severe psychological distress (including suicidal ideation)—research coordinators and the study data system*

Given the difficult situations faced by COVID patients, we recognize that there is a slight risk that some participants may become distressed completing questionnaires or viewing study materials, as mentioned above. Additionally, given the extreme stresses of the critical illness experience, participants may even endorse suicidal ideation. We will take the following measures to prevent any negative reactions as well as effectively manage any serious distress that occurs:

- (1) All of the in-person and telephone-based data collection sessions will be conducted by highly trained research coordinator professionals who are sensitive to the issues that arise.
- (2) Clinical research coordinators will emphasize to participants that any interviews or other study interactions are participant-controlled. Thus, participants will be instructed that they are in control over what they share and generally how long they discuss any topic that is addressed.
- (3) Participants will be told that they can discontinue an interview at any time and that they are also free to reschedule an interview or treatment session at any time within the week.
- (4) Overall, we are very sensitive to the common and pervasive nature of psychological distress among COVID survivors and are experienced in discussing these issues with them. There is also a potential risk for identifying underlying mental health issues through the LIFT sessions, telephone calls, and survey responses. For issues such as passive suicidal ideation or symptoms of depression, anxiety, or PTSD, an informational sheet will be provided with contact numbers for additional mental health services. Additionally, at the beginning of the program, all subjects will be informed that the training program may uncover unresolved and distressing thoughts or feelings; and a list of resources will also be provided at that time.

(5) As a safety measure that we have used in past/current clinical research, the study team will be trained to monitor participants closely beyond just the parameters of questionnaire scores. The study staff, including the trained clinical research coordinators and the therapist, will monitor participants closely during any interviews performed and will refer those with any concerning level of emotional distress and/or relationship distress to the PI to evaluate by phone. This will be done immediately, particularly if there is staff concern about a participant who indicates suicidality. Point #6 below describes PI actions that will follow.

(6) We have developed a specific protocol to manage any study participant who expresses suicidal thoughts in person, by telephone, or via the app at any point during the study. All study participants will be informed of this suicidality response plan prior to signing the informed consent for their participation in the study. The PI or trained CRC will complete the online Columbia Suicide Severity Rating Scale (C-SSRS) training, a 30-minute interactive slide presentation followed by a question-answer session. The C-SSRS is scale that can delineate high, moderate, and low-risk levels.

Our Suicidality Response Plan can be activated in two main ways.

First, study staff (coordinators, therapists, investigators, PI) may have in-person or telephone interactions that concern them.

Second, the study app system will automatically detect any endorsement of active suicidal intent in a 2-step process that is contingent on the PHQ-9's item #9 (which evaluates suicidal thoughts) and the C-SSRS item #4 (which evaluates intent by asking: *Have you had these thoughts and had some intention of acting on them?*) as shown here:

PHQ-9 item 9 response	Suicidal intent item response	Action by app system	Action by team
0	n/a	n/a	n/a
1, 2, or 3 (i.e., ≠ 0)	NO	n/a	n/a
1, 2, or 3 (i.e., ≠ 0)	YES	Alert to study manager, therapist, and PI	Immediately contact participant

If the participant is deemed to be at high risk for active suicidality based on direct interaction or the PHQ-9 item plus the C-SSRS item response, the app system will send an alert email and/or text message in real time to the study manager, the study therapist, and relevant site PI (no PHI included, only study ID). One of these study staff will then immediately contact the participant. Using the full C-SSRS, the trained staff will then help to assess the participant to determine if they endorse active suicidal ideation. The trained staff will also determine if the participant is currently being treated by a mental health professional.

If the participant is considered to be actively suicidal then at least one of the following plans will be followed depending on the location of the participant for each of the following situations:

Situation 1. If the participant is with one of the study personnel [not expected to occur in the RCT]:

a. The study personnel will notify the PI immediately

b. The study personnel will either physically walk the subject to the emergency department, or call a Psychiatric Emergency services number relevant to the site as described above.

Situation 2. If the participant is on the telephone:

a. The study personnel will notify the PI immediately.

b. The study personnel will stay on the telephone with the subject participant.

c. The study personnel will immediately contact 911 to initiate an on-site rescue if such action is clinically indicated.

d. The study personnel will stay on the telephone with the subject until EMS services have contacted the participant.

Situation 3. If there are any active suicidal concerns in any of the surveys (e.g., PHQ-9 above):

- a. The study data system will notify the PI and Study Manager immediately.
- b. The study personnel will then contact the honest broker to de-identify the participant information.
- c. Next, the study personnel will contact the participant by telephone.
- d. The study personnel will stay on the telephone with the subject participant.
- e. The study personnel will use a different telephone line to immediately contact 911 to initiate an on-site rescue if action is clinically indicated.
- f. The study personnel will stay on the telephone with the subject until EMS services have contacted the participant.

If the participant is determined to be actively suicidal and require immediate medical therapy, they will be withdrawn from the study.

If the patient is deemed not to be actively suicidal, they will be given contact information for the National Suicide Prevention Lifeline ([name]), a free, 24-hour hotline available to anyone in suicidal crisis or emotional distress. This will occur via the app for the intervention group and via email for control participants.

(7) As described in above, all concerns about participant safety will be discussed immediately with the PI including concerning, severe distress that does not involve suicidality. For these situations, once an “alert situation” is known, the PI will refer the participant if needed (based on a PI-led phone call) to local psychological resources as we have done previously with this well-tested Distress Management Protocol used successfully by [name] in 3 past clinical trials involving family members that used psychological distress outcomes. We will also make urgent and emergency referrals as needed based on information learned by any site PI on a site-by-site basis (see contact information above). It is important to note that this system has been developed in full partnership with the Duke IRB, who approve it in its entirety and have described it as a model for future patient safety in Duke-based clinical research. To date based on these studies that have included over 400 participants, we have found that <5% of participants will require a call from the PI during some point in the study period. Of those, none have required referral to acute psychiatric care after a detailed interview from the PI. After a disposition / solution has been made, both the resolution (and follow up) will be documented in the ‘contact log’ section of the data system for reporting to the DSMB.

(8) Finally, though there were no patient deaths during the LIFT COVID RCT follow-up period, we recognize that we are working with a seriously ill population that is at risk for death during follow up due to their underlying illness. We are very sensitive to issues surrounding patient death in relation to study procedures and interviews. We have dealt with this respectfully for years in our studies involving in-person, telephone, and app-based interviews and surveys. On phoning any participant, we will initiate a conversation in a sensitively scripted manner to tactfully ascertain the patient’s vital status should a family member answer first. If the patient has died, we will provide brief support. If a patient states that they wish to drop out, we will respect that as well.

Vulnerable populations. We will not enroll patients from vulnerable populations (e.g., imprisoned persons, minors).

Adverse events (AEs), serious adverse events, (SAEs) and unanticipated problems (UPs). Our plan for AEs, SAEs, and UPs has been reviewed and accepted by the NIH. As mentioned before, we recognize that there is a slight risk that some participants may become distressed when completing self-report measures or participating in interviews. In our previous studies using similar self-report surveys (telephone, in person, or ePRO), we have encountered little resultant distress. In fact, many participants have reported that they were relieved to be able to have a platform through which to reflect on such issues. When necessary, participants who experience psychological distress related to completing questionnaires will be referred for appropriate

Pro00106306: Addressing psychological distress symptoms among serious illness survivors of a viral pandemic with a completely self-directed, symptom-responsive mobile mindfulness intervention

psychiatric or psychological care. All participants will have access to a PI's mobile phone number available 24 hours a day (shown in the consent form). If a telephone interview is required, it will be conducted by an experienced interviewer who has been trained to be sensitive to the nature of these issues.

In this trial, we expect AEs to be extremely uncommon because it is a behavioral trial. However, it is possible that participants could become distressed in an ICU setting in the event that their loved one dies or becomes more ill. One particular symptom of note that will be considered an AE and reported to the IMC will be suicidal ideation as operationalized by responding to PHQ-9 item #9 (Thoughts that you would be better off dead or of hurting yourself in some way) with either 'more than half the days' or 'nearly every day' out of the preceding 2 weeks. In this trial, we do not anticipate any SAEs because it is a behavioral trial. A SAE in this trial would include a suicide attempt, a hospitalization, or death. All serious adverse events will be reported within the standard timelines required to these bodies as well as to the OHRP and the NIH/NCCIH. AEs and SAEs will be reported to these agencies per their standard guidelines.

While we do not anticipate any UPs because it is a behavioral trial that focuses on ICU patients, critical illness and its recovery process are unpredictable. Unanticipated problems will be identified, discussed by the PIs, and resolved by group consensus. Therefore, should there be unanticipated problems observed we propose the following reporting process—itself framed by NIH guidelines. First, the PIs and Duke University will include a written report that will be submitted to the NCCIH, the study DSMB, and the Central IRB that will describe the UP, the context, and the proposed corrective plan. This written report will be provided within 1 week (unless it/they is/are also an SAE, in which case the timeline for SAE reporting will be followed). The UP will also be forwarded OHRP using [[contact]](mailto:[contact]) within two weeks of the event.

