## **7. Data Collection**

### **7.a. BLUE CORAL data collection**

BLUE CORAL includes data collection from enrolled patients' clinical records. There are three types of forms for each study: admission (hospital / study day 1), daily, and discharge.

The case report form (CRF) is built in REDcap which can be imported as a local instance or centrally through the PETAL CCC. Since there may be times when study personnel are mandated to work from

home due to the ongoing pandemic, BLUE CORAL has many study procedures that are designed to allow off-site completion. All elements that contribute to the COVID ordinal outcome scale are included in daily and summative data collection. Manual data entry of all elements into REDCap may not be required depending on the site's ability to extract data from the EMR.

The BLUE CORAL study will obtain pre-hospital information from patients or their caregivers before hospital discharge. The survey consists of questions regarding functional status and health-related quality of life. PETAL study staff members are familiar with the conduct of these surveys as they were used successfully in the ROSE RCT. With high severity of illness, infection control precautions, and absence of family visitation, we anticipate that survey completion will be difficult. Therefore, we have developed multiple approaches to survey completion (telephone, tablet computer, or email with either patients or families) and will attempt to complete as able.

BLUE CORAL patients who survive hospitalization, speak English, are domiciled, and did not have severe dementia or severe disability before hospitalization may be eligible to enter the post-hospital follow-up study (BLUE CORAL). This study will be conducted by the FUNCTION team at the University of Michigan, led by [name], using protocols developed and executed in the PETAL Network ROSE and ongoing CLOVERS studies. Sister sites, Oregon Health & Sciences University (OHSU) and University of Colorado-Denver, led by Drs. [name] and [name], respectively, may be asked to conduct the study visits as needed. Post-hospital follow-up will occur by telephone at 1, 3 and 6 months after hospital discharge (Table 1). Patients will provide consent for continued involvement at the time of the first call.

Table 1: Data collection timing and content for BLUE CORAL and LIFT RCT participants.					
	Hospital	1 month* (T1)	During intervention 	3 months* (T2)	6 months* (T3)
Contact info	X	X		X	X

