### 7.b. LIFT COVID Surveys

As shown in Table 1, participants enrolled in the LIFT COVID intervention arm will also complete the PHQ-9 survey weekly within the LIFT mobile app for the duration of the 4-week intervention.

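### Situation 3 of the Suicidality Response Plan can be read as placing an honest broker, who is on no alert list, between an ID-only alert and the call, and it names the wrong operation for the broker

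*Combined protocol and SAP*

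**What the plan says.** Section 7.b says that intervention participants "will also complete the PHQ-9 survey weekly within the LIFT mobile app for the duration of the 4-week intervention". Under item (6) of the oversight plan in section 15, the app raises an alert when PHQ-9 item 9 is above zero and the follow-up question on intent is answered yes.

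The plan describes what happens next in several places:

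- **Alert table.** The system action is "Alert to study manager, therapist, and PI", and the team is to contact the participant at once.
- **Narrative after the table.** A real-time message goes to the study manager, the study therapist and the "relevant site PI (no PHI included, only study ID"). Then: "One of these study staff will then immediately contact the participant".
- **Situation 3.** For concerns in any survey, with the PHQ-9 as the example, step a is "The study data system will notify the PI and Study Manager immediately". Step b is "The study personnel will then contact the honest broker to de-identify the participant information". Step c, introduced as the next action, is the telephone call.
- **Reporting Procedures (section 15).** For the PHQ-9 suicidal ideation item, the team will telephone the participant and assess the situation. No broker is mentioned.

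Situation 2 applies "If the participant is on the telephone" and involves no broker. The scheduled interviews are by telephone: "Post-hospital follow-up will occur by telephone at 1, 3 and 6 months after hospital discharge".

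**The concern.** This is an emergency rule, and its wording can be followed in more than one way. Taken literally as the route from alert to call, Situation 3 makes the call wait on a person who did not receive the alert and whose contact route and hours are not given. It also tells staff to have that person remove identifiers when they need a name and a telephone number.

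This matters most for the in-app survey. There, a participant may report intent to act through a self-directed app with no staff member on the line. In a telephone interview someone is already speaking to the participant, so Situation 2 normally fits. What is at stake is the speed of a safety response, not any property of the trial's inference.

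**Working it through.** No formula applies and the plan gives no figure to reproduce. The check compares the texts.

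**1. Recipient lists**

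| Source | Study manager | Therapist | PI | Honest broker |
|---|---|---|---|---|
| Alert table | yes | yes | yes | no |
| Narrative | yes | yes | yes (site PI) | no |
| Situation 3, step a | yes | no | yes | no |

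The broker is on 0 of 3 lists, the therapist on 2 of 3, and the study manager and PI on 3 of 3. The broker appears only in step 3b.

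**2. Order of steps.** The table and narrative go from alert to immediate contact. Situation 3 goes from notification to broker to call, and its connecting words make the order sequential.

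**3. Direction of the broker's task.** The input to step 3b is an alert with a study ID and no identifying data. The output needed for step 3c is a telephone number. The operation between them is to restore identity. The document does not use the word *re-identify*; it is inferred from the steps on either side.

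**4. Is Situation 3 the alert-to-call path?** Two features say yes: step a is the system notification and step c is the call. The heading's reference back to the PHQ-9 supports this. One feature says no: the sentence introducing Situations 1 to 3 applies them once a participant has been judged actively suicidal, which in the narrative follows contact and a full C-SSRS assessment. That sentence also requires only one or more of the plans, so Situation 2 could apply alone once the participant is on the line. Both readings are available.

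**5. Can an alerted person look up the number without a broker?** An ID-only alert always needs a look-up. The Privacy paragraph in section 15 says that IDs are linked to names in a separate app subsystem, that telephone numbers are open to trained staff on the delegation log, and that the PIs have no password to view the database. Whether that last restriction covers the contact subsystem is not stated. Section 8 has delegated staff entering contact information, and section 16.b has study personnel using a tracking application for the contact log. None of these says that a study manager, therapist or site PI can go from ID to telephone number when an alert arrives. The RDSP and the delegation log, which would settle this, were not supplied.

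**The case against.** The best reply is that the plan is staged. The narrative governs the alert and requires immediate contact; Situations 1 to 3 are response plans for someone already assessed. On that reading the broker never stands before the first call. This has real force, and it is why the text should be called ambiguous and not simply contradictory. It does not fully succeed, because a plan that starts with a system notification and then places a call reads poorly as something that follows contact.

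A second reply is that the table and narrative are silent on the look-up while Situation 3 supplies it, perhaps as a deliberate privacy control that also serves PIs without database access. That may be so. Staff can also contact a broker who is on no alert list, and trained staff would probably understand the intended verb.

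Safeguards exist. The Reporting Procedures provide a broker-free call. Section 17 has the Study Manager monitoring the weekly PHQ-9 safety system as a redundant check. Participants have a PI number at all hours, and section 4.b excludes suicidal ideation at the 1-month interview.

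Stronger inferences are tempting but unsupported:

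- **That calls will be delayed.** This depends on access rights not shown, and no broker response time is given.
- **That the therapist goes unalerted.** Step 3a omits the therapist but does not cancel the narrative's alert.
- **That a number of affected participants can be given.** Counts of scheduled surveys are not counts of alerts. The under-5% rate of PI calls in section 15 most naturally refers to severe distress without suicidality, in earlier trials involving family members.
- **That telephone-survey concerns should go to Situation 2 only.** Participants may end an interview at any time, and Situation 3 then provides the call-back.

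**Conclusion.** The point holds as a defect of wording and sequence in a safety procedure. Three things are certain from the text: *de-identify* is the wrong operation before a call, the broker is on no recipient list and is undefined, and step 3a's recipients differ from those in the table and narrative. That the call waits for the broker is one of two available readings. It assumes that Situation 3 is the alert-to-call path and that no alerted role already holds the link to the telephone number.

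Any delay is possible but cannot be quantified, and its size should not be estimated from the documents. There is no effect on estimand, analysis or power. The change is worth making because it costs little and the situation it covers is grave.

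**What to change.** 1. In step 3b, for as long as it stands, replace *de-identify* with *re-identify*.
2. Make step 3a's recipients match the table and narrative: study manager, therapist and site PI.
3. Choose one route for the look-up. Either give at least one alerted role standing access to the link from study ID to telephone number (or confirm that it exists) and delete step 3b; or keep the broker and send the broker the alert at the same moment as the others, so that the look-up does not hold up the call.

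Either route in item 3 removes the broker as a sequential hold-up, whichever way the introductory sentence is read. Leave Situation 3's coverage of all surveys, and the steps after contact, as they are.

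The cost is a few words of protocol text plus, if not already in place, one access permission or one extra alert address. The small downside is that one more delegated person may be able to link study IDs to contact details.
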